1. STUDY DESIGN

In this study we will evaluate the application of ESWT for patients with DU/UAB. ESWT with 2500 shocks, frequency of 4 pulses per second and maximum total energy flow density 0.25 mJ/mm² or placebo (Shock Wave setting without shock wave energy transmission) will be applied to the suprapubic bladder region once a week for 6 weeks. Treatment parameters were modified from different urologic and nonurologic case studies and publications. The device used for the study was a standard electromagnetic shock wave unit with a focused shock wave source (LITEMED LM-ESWT-mini system, Taiwan). The focus zone penetration depth was in the range of 30–90 mm. This study was designed in a single center, randomized, double-blind, placebo-controlled trial to test the actual therapeutic effects of ESWT on DU/UAB. The results of this study may provide clinical evidence for an alternative therapeutic regimen in the treatment of DU/UAB.

2. OBJECTIVE AND ENDPOINTS

The objective of this study is to evaluate the efficacy and safety of ESWT for the treatment of DU/UAB.

The primary and secondary endpoints are described as shown below:

(1) Primary End-point (1 month)

The efficacy of LESW will be evaluated for:

Net changes of the mean post void residual (PVR) volume (mL) from baseline to 1 month after the treatment day.

(2) Secondary end-points

Efficacy

The efficacy of ESWT will be evaluated for:

- (1) Net changes of the following parameters from baseline to 1 month after the treatment day: functional bladder capacity (FBC), voiding frequency at daytime and voiding frequency at night time, incontinence, as record in 3-day voiding diary.
- (2) Global response assessment (GRA) of satisfaction by the patient (categorized into -3, -2, -1, 0, 1, 2, 3, indicating markedly worse to markedly improved) at 1 month after the last treatment day. An improvement of GRA by 2 scales at 1 months is considered effective.
- (3) Net changes of the maximum flow rate, voided volume, Pdet@Qmax, and postvoid residual volume from baseline to 1 month after the treatment day.

(4) Changes of Underactive Bladder Questionnaire (UAB-Q) score.

(5) Changes of urinary nerve growth factor and cytokines level from baseline to 1 month after treatment day.

Safety

(1) Local adverse event incidences (hematuria, miction pain, UTI, urinary retention). The severity of adverse event is categorized as indicated below:

Severity of AE	Description
Mild	Transient and easily tolerable, not affecting usual daily activities
Moderate	Causes patient's discomfort, interrupting usual daily activities
Severe	Causes considerable interference with daily activities and may be incapacitating or life-threatening

(2) Systemic Adverse Events:

Any systemic adverse event occurring after ESWT will be asked to report and patients will be properly investigated and treated. The cause for systemic adverse event may be not related with ESWT.

(3) Changes in physical examinations.

(4) Changes in blood pressure and other laboratory test results will be examined if patients have severe adverse events or physical examinations reveal abnormalities.

(3) Follow-up (3 months)

Efficacy

The efficacy of ESWT will be evaluated for:

- (1) Net changes of the following parameters from baseline to 3 month after the treatment day: functional bladder capacity (FBC), voiding frequency at daytime and voiding frequency at night time, incontinence, as recorded in 3-day voiding diary.
- (2) Global response assessment (GRA) of satisfaction by the patient (categorized into -3, -2, -1, 0, 1, 2, 3, indicating markedly worse to markedly improved) at 3 month after the last treatment day. An improvement of GRA by 2 scales at 3 months is considered effective.
- (3) Net changes of the maximum flow rate, voided volume, Pdet@Qmax, and postvoid residual volume from baseline to 3 months after the treatment day.
- (4) Changes of Underactive Bladder Questionnaire (UAB-Q) score.
- (5) Changes of urinary nerve growth factor and cytokines level from baseline to 3 months after treatment day.

Patients who are not effective to the treatment at 3 months will receive repeated ESWT treatment.

Safety

- (1) Local adverse event incidences (hematuria, miction pain, UTI, urinary retention) are reported.
- (2) Any systemic adverse event occurring after ESWT will be asked to report and patients will be properly investigated and treated. The cause for systemic adverse event may be not related with ESWT treatment.

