5.2. Study Visits and Evaluations

5.2.1. Screening Visit (V0, 2 weeks before the treatment day)

- 5.2.1.1. Explain the nature of the study and have patients to read and sign an Informed Consent Form.
- 5.2.1.2. Screen patients for inclusion/exclusion criteria (section 4.2 and 4.3).
- 5.2.1.3. Medical History of DU/UAB and previous treatment modalities.
- 5.2.1.4. Vital signs monitoring and general physical examinations of all systems, EKG examination to rule out abnormal cardiac diseases, and biochemistry examinations including CBC, PT, APTT, ALT, AST and Cr.
- 5.2.1.5. Check Uroflowmetry and record, urodynamic study and PVR volume.
- 5.2.1.6. Urinalysis for WBC, RBC, pH, Protein, Glucose and Bacteria if patient has symptoms suggestive of urinary tract infection.

5.2.1.7. Physical assessments to exclude bladder outlet obstruction or bladder pathology.

5.2.1.8. Record concomitant medication.

5.2.1.9. Dispense three-day voiding diary to record for 3 days before the treatment day.

5.2.1.10. Record UAB symptom score.

5.2.1.11. Discontinue all previous UAB-related medication.

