5.2.2.2 Inform patient of the possible adverse events

5.2.2.3 Review three-day voiding diary.

5.2.2.4 Collect 30 ml urine for analysis of the urinary NGF and cytokines levels.

5.2.2.5 ESWT given.

5.2.3. Treatment Visit (V2, Week 1, 1 week \pm 3 days after the V1 treatment day)

5.2.3.1 Vital signs monitoring, and confirm eligibility of patients.

5.2.3.2 ESWT given.

5.2.4. Treatment Visit (V3, Week 2, 1 week \pm 3 days after the V2 treatment day)

5.2.4.1 Vital signs monitoring, and confirm eligibility of patients.

5.2.4.2 ESWT given.

5.2.5. Treatment Visit (V4, Week 3, 1 week \pm 3 days after the V3 treatment day)

5.2.5.1 Vital signs monitoring, and confirm eligibility of patients.

5.2.5.2 ESWT given.

5.2.6. Treatment Visit (V5, Week 4, 1 week \pm 3 days after the V4 treatment day)

5.2.6.1 Vital signs monitoring, and confirm eligibility of patients.

5.2.6.2 ESWT given.

5.2.7. Treatment Visit (V6, Week 5, 1 week \pm 3 days after the V5 treatment day)

5.2.7.1 Vital signs monitoring, and confirm eligibility of patients.

5.2.7.2 ESWT given.

5.2.7.3 Dispense three-day voiding diary to record for 3 days before the next visit day.

5.2.8 Evaluation Visit I (Primary end-point, V7, 4 weeks \pm 3 days after the V6 treatment day)

5.2.8.1 Review patients voiding diary for urinary frequency, functional bladder capacity, and record reported UAB symptom score, and GRA.

5.2.8.2 Vital signs monitoring and record adverse events.

5.2.8.3 Check urinalysis for urinary tract infection if patient has symptoms.

5.2.8.4 Check uroflowmetry for maximum flow rate, voided volume, and PVR volume.

5.2.8.5 Appointment for the next visit at 12 weeks \pm 3 days after the V6.

5.2.8.6 Dispense three-day voiding diary to record for 3 days before the next visit day.

5.2.8.7 Collect 30 ml urine for analysis of the urinary NGF and cytokines levels.

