- (1) Local adverse event incidences (hematuria, micturition pain, UTI, urinary retention) will be reported by both treatment group and controlled group and by physiological systems as appropriate. Incidence of adverse events and the categories of adverse event severity between treatments will be analyzed. The coding system used will be COSTART.
- (2) The abnormalities of laboratory test results will be reported by patient list in the patients who have been tested for having severe adverse event.
- (3) The changes in physical examinations will be presented in the by-patient list.
- (4) All statistical tests used will be two-tailed with α = 0.05.

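### Change in physical examination is a 1-month safety endpoint, but no examination is scheduled after screening, and the SAP laboratory listing leaves out examination-triggered tests

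*Protocol*

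**What the plan says.** **Endpoint.** Item (3) of the 1-month safety list in Protocol section 2 is "Changes in physical examinations". SAP 7.2, safety item (3), commits to the output: "The changes in physical examinations will be presented in the by-patient list".

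**Schedule.** Protocol 5.2.1.4 (V0) calls for "general physical examinations of all systems", and 5.2.1.7 adds a physical assessment for eligibility at the same visit. At the 1-month visit (V7), line 5.2.8.2 reads "Vital signs monitoring and record adverse events", with no examination.

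**Laboratory data.** Protocol section 2, safety item (4), says: "Changes in blood pressure and other laboratory test results will be examined if patients have severe adverse events or physical examinations reveal abnormalities". SAP 7.2, safety item (2), says: "The abnormalities of laboratory test results will be reported by patient list in the patients who have been tested for having severe adverse event".

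**The concern.** A change needs a baseline value and a later one. The schedule supplies only the baseline. Any later findings would come from examinations done because something had happened to the patient, so the listing would reflect who was examined and why. It would not show what was found in each arm on a common footing.

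The gap also reaches laboratory safety data. The blood tests (CBC, PT, APTT, ALT, AST, Cr) are scheduled only at V0. After that, apart from symptom-driven urinalysis and the general investigation of systemic events, the stated routes to laboratory results are the two triggers in section 2. One of them depends on an examination that the schedule does not contain. The SAP listing then omits that route altogether.

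**Working it through.** The plan gives no figure on this point, so the check is a reading of the endpoint list, the schedule and the SAP outputs against each other.

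**Step 1: which visits carry an examination (Protocol 5.2).**

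| Visit | Contents relevant here | Examination? |
|---|---|---|
| V0 | Vital signs, general examination, eligibility assessment, blood tests | Yes |
| V1 | Randomization number, information on adverse events, diary review, urine sample, treatment | No |
| V2 to V6 | Vital signs, eligibility check, treatment (diary handed out at V6) | No |
| V7 (1 month) | Diary, symptom score, GRA, vital signs, adverse events, urinalysis if symptomatic, uroflowmetry and PVR, urine sample | No |
| V8 (3 months) | As V7, plus urodynamics | No, and none is promised |

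Sections 3 and 5.1 add vital signs around each treatment, and 5.1 adds a question about pain. Neither adds an examination.

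**Step 2: the count for the 1-month endpoint.** From V0 to V7 there are 8 visits, and 1 has an examination. From V1 to V7 there are 7 visits, and 0 have one. With change = (value after baseline) − (value at V0), the first term is not scheduled for any patient in either arm. That is 0 of the approximately 60 patients to be enrolled.

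**Step 3: V8.** The 3-month safety list in section 2 has two items, local and systemic adverse events. It makes no claim about examination, so V8 is left out of the count.

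**Step 4: laboratory triggers against the SAP listing.**

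| Reason for the test | Foreseen in Protocol section 2, item (4)? | In the SAP 7.2 listing, item (2)? |
|---|---|---|
| Severe adverse event | Yes | Yes |
| Abnormal examination without a severe adverse event | Yes | No |

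The SAP limits the listing to results "in the patients who have been tested for having severe adverse event", while section 2 says they "will be examined if patients have severe adverse events or physical examinations reveal abnormalities". The second row is the mismatch. It stands whatever is decided about the schedule, because an unscheduled examination can also lead to a test.

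**Step 5: blood pressure.** Item (4) names blood pressure too, but sections 3 and 5.1 have it recorded before and 30 minutes after treatment, and vital signs are taken at V7 and V8. These data do not depend on either trigger.

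**The case against.** The best defence is that examinations will take place even though no line of the schedule names them. Section 2 says that systemic adverse events will be properly investigated. Staff must confirm eligibility at V2 to V6, and some criteria, such as prolapse beyond the introitus, are clinical. Item (4) does not require the examination to be a scheduled one. The output is also only a by-patient listing, with no between-group test or estimate of examination change.

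Much of this stands. A reader might infer that the endpoint and the laboratory trigger cannot be delivered at all. The documents do not support that: an unscheduled examination could supply a finding and set off a test, and the severe-event trigger works as written. The defence does not supply systematic data, however. The eligibility check is undefined, and event-driven examinations cover only patients who had an event.

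Three other stronger readings also fail:
- **Blood pressure follow-up is lost.** It is recorded routinely, as step 5 shows.
- **V8 needs an examination as well.** The 3-month safety list does not claim one.
- **The trial report would say that examinations and laboratory results had both been assessed.** Nothing in either document says what the report would state.

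**Conclusion.** The plan is wrong as written, at minor severity. It states a 1-month safety endpoint and an SAP output for which 0 of the 7 visits from V1 to V7 schedule the measurement. Separately, the SAP laboratory listing covers one of the two triggers that the Protocol names.

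The consequence is confined to descriptive safety listings. The primary PVR analysis and the sample size do not depend on it.

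The conclusion assumes that the visit-by-visit lists in section 5.2 are the full schedule. Nothing is inferred from pages that were not available. How many examination-triggered tests would go unlisted cannot be estimated, because the documents give no rate for them.

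**What to change.** 1. **Endpoint and schedule.** Make Protocol section 2, section 5.2 and SAP 7.2, item (3), agree on the 1-month examination. One way is to record it at the existing V7 visit, in line 5.2.8.2. Another is to stop claiming safety endpoint (3) and its listing. V8 need not change.
2. **Trigger wording.** Reconcile section 2, item (4), with the schedule, so that it is clear which examinations it refers to. What the trigger should be is for the investigators to decide.
3. **SAP 7.2, item (2).** List abnormalities from all post-baseline laboratory tests, whatever triggered them, and preferably show the reason for each test in the listing.

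The cost is a few minutes at one visit already planned, or the removal of one endpoint, plus one line in the SAP. No new visit or staff is needed. It is best settled before patients reach V7, because an examination that was not done cannot be recovered later.

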3. SHOCK WAVE MACHINE AND PROCEDURES

The shock wave applicator, FS-I (“LITEMED” LM-ESWT-mini system, Taiwan), will be gently placed on the skin area over the bladder dome, right upper lateral wall, right lower lateral wall, left upper lateral wall, and left lower lateral wall during once a week for 6 weeks, with 2500 shocks, frequency of 4 pulses per second, and maximum total energy flow density 0.25 mJ/mm². The current shock wave intensity and number used was followed from reference [1].

Eligible patients will be assigned a randomization number in sequential order and each of the randomization will determine the allocation of one of the two treatment groups (ESWT and Placebo) in 1: 1 ratio as shown below. The ESWT and placebo will be controlled by a research assistance who will not evaluate the therapeutic outcome to ensure the double-blind method.

Vital signs (body temperature, blood pressure, heart rate and respiration rate) will be recorded at pre-treatment and 30 minutes following treatment.

The treatment will be carried out in the out-patient clinic. Patient will be stayed in a treatment room and accompanied by a research assistant.

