5. STUDY PROCEDURE

5.1. General Study Design

This study is designed as a double-blind, randomized, paralleled, controlled trial. The DU/UAB confirmed patients will be randomly assigned to receive (1) ESWT or (2) placebo control group. The treatments will be evaluated at baseline screening and at least 2 study required visits (treatment visit and primary end-point evaluation visit) will be performed for PVR, symptom score recording, urodynamic studies, adverse event recording and global satisfaction assessments. Urine samples (30 ml) will also be collected at each visit for analysis of the urinary NGF and cytokines levels.

Procedures of LESW

Studied patients are requested to void completely before treatment. Urine samples (30 ml) will be collected for analysis of the urinary NGF and cytokines levels. The patients are placed in supine position in an examination room at out-patient clinic.

The shock wave applicator, FS-I (“LITEMED” LM-ESWT-mini system, Taiwan), will be gently placed on the skin area over the bladder dome, right upper lateral wall, right lower lateral wall, left upper lateral wall, and left lower lateral wall during once a week for 6 weeks, with 2500 shocks, frequency of 4 pulses per second, and maximum total energy flow density 0.25 mJ/mm². The current shock wave intensity and number used was followed from reference [1].

Patients will be asked about any painful sensation that they experience during the treatment. Vital signs (body temperature, blood pressure, heart rate and respiration rate) will be recorded at pre-treatment, and 30 mins following treatment. During the treatment, patient will be stayed in a treatment room and accompanied by a research assistant.

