5.2.9 Evaluation Visit II (V8, 12 week \pm 7 days after the V6)

5.2.9.1 Review patients voiding diary for urinary frequency, functional bladder capacity, and record reported UAB symptom score, and GRA.

5.2.9.2 Vital signs monitoring and record adverse events.

5.2.9.3 Check urinalysis for urinary tract infection if patient has symptoms suggestive of urinary tract infection.

5.2.9.4 Perform Uroflowmetry study for maximum flow rate, urodynamic study and PVR volume.

5.2.9.5 Collect 30 ml urine for analysis of the urinary NGF and cytokines levels.

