6.3. Serious Adverse Event

Serious adverse events are defined as any finding which suggests a significant hazard, contraindication, side effect, or precaution.

Additionally, any adverse event which the consequence is:

- Fatal

- Life threatening

- Permanently disability or incapacity

- Requiring hospitalization or prolonging a current hospitalization

- A congenital abnormality

Serious, alarming and/or unusual adverse events must be reported to the following individual within 24 hours of the investigator's knowledge of the event.

An Adverse Event Form should be completed for all serious adverse events and forwarded to the ADR within 24 hours. When new significant information is obtained as well as when outcome of an event is known, the investigator should inform the ADR. In applicable cases, ADR may request a letter from the investigator summarizing events related to the case. Investigators should follow patients as far as possible until an outcome to the events is known.

The investigator is responsible to communicate details of medical emergencies in trial patients to the ethics Committee.

REFERENCES

3. Astellas Pharma Inc (Astellas Pharma Europe B.V.). A Study of ASP8302 in Participants With Underactive Bladder. ClinicalTrials.gov Identifier: NCT03702777. <https://clinicaltrials.gov/ct2/show/NCT03702777?term=NCT03702777&draw=2&rank=1>

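### Vital signs are recorded routinely, but blood-pressure change is examined only after a trigger and no by-arm summary is planned; some laboratory results also have no planned report

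*Protocol*

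**What the plan says.** **Collection.** Protocol Section 3 states: "Vital signs (body temperature, blood pressure, heart rate and respiration rate) will be recorded at pre-treatment and 30 minutes following treatment". Section 5.1 repeats the rule. Neither makes it depend on an event. In Section 5.2, each of the treatment visits V2 to V6 lists "Vital signs monitoring, and confirm eligibility of patients", and the evaluation visits V7 and V8 each list "Vital signs monitoring and record adverse events". The list for V1, the first treatment visit, has no vital signs.

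**Use.** Protocol Section 2, Safety (4), states: "Changes in blood pressure and other laboratory test results will be examined if patients have severe adverse events or physical examinations reveal abnormalities".

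**SAP.** Section 7.2 analyses the incidence and severity of adverse events between treatments. Physical-examination changes go into a by-patient listing. Laboratory abnormalities "will be reported by patient list in the patients who have been tested for having severe adverse event". Neither blood pressure nor any other vital sign is mentioned. The commitment to point estimates with 95% confidence intervals covers efficacy variables only.

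**Severe and serious.** Protocol Section 2 grades severity by interference with daily activities. Section 6.3 defines seriousness by consequence, for example "Requiring hospitalization or prolonging a current hospitalization".

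**The concern.** Safety is part of the study objective, and SAP 7.2 sets out to confirm the safety profile in both groups. A reading before and another 30 minutes after treatment, in a 1:1 sham-controlled trial, is well suited to showing an acute effect on blood pressure or heart rate. If blood-pressure change is examined only in patients with a severe event or an abnormal examination, the patients examined are chosen by something that happened after randomisation. The denominator is then lost, and a comparison within that subset is no longer a randomised one. The adverse-event comparison does not fully replace it, because a modest average shift need not appear as a reported event.

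The laboratory listing raises a related problem. Section 2 names two prompts for examining laboratory results, and the SAP reports results from only one of them.

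**Working it through.** **1. The plan's own figure.** SAP 7.4 gives 24 per group, a difference of -50.0 mL, SD 60.0 and two-sided alpha 0.050. The noncentrality is 50 / (60 × √(2/24)) = 2.887 with 46 degrees of freedom. Power is 80.677%, as stated. Enrolment is 48 / 0.80 = 60, also as stated. Neither figure bears on this point.

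**2. The rules side by side.**

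| Data | Collected | Planned use |
|---|---|---|
| Vital signs around treatment | Unconditional (Protocol 3, 5.1) | Blood-pressure change only if triggered (Protocol 2); nothing in the SAP |
| Vital signs at V7, V8 | Listed in the visit schedule | As above |
| Laboratory results after V0 | Not scheduled; two triggers (Protocol 2) | Listed for one trigger only (SAP 7.2) |
| Adverse events | All | Incidence and severity by treatment (SAP 7.2) |

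**3. Amount of blood-pressure data.** Treatment "will be applied to the suprapubic bladder region once a week for 6 weeks", so there are 6 sessions. If the before-and-after rule applies at each, a patient has 6 × 2 = 12 readings. That is 12 × 60 = 720 readings (360 pairs) in 60 patients, or 12 × 48 = 576 (288 pairs) in 48. If V1 has none, as its visit list suggests, 60 patients give 5 × 2 × 60 = 600. Readings at V7 and V8 are additional.

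**4. Share examined.** The documents do not say how many patients would meet either trigger. The rates below are assumptions covering both triggers together. The chance that a given arm of 30 has no such patient is (1 − r)^30.

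| Assumed share r | Expected patients of 60 | Chance a given arm has none |
|---|---|---|
| 2% | 1.2 | 55% |
| 5% | 3 | 21% |
| 10% | 6 | 4% |
| 20% | 12 | 0.1% |

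**5. Precision if all patients are summarised.** For one before-to-after change, the 95% half-width for the arm difference is t × √(2/n) × SD.
- 30 per arm: 2.002 × 0.258 = 0.52 SD.
- 24 per arm, after the planned 20% dropout: 2.013 × 0.289 = 0.58 SD.

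For an assumed SD of 10 to 15 mmHg, which the documents do not give, the standard error is 2.6 to 3.9 mmHg with 30 per arm and 2.9 to 4.3 mmHg with 24.

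**6. Laboratory results with no planned report.** Protocol 5.2 schedules biochemistry only at V0, so later results arise because something prompted them. The SAP listing covers patients tested because of a severe event. Two kinds of result fall outside it: those prompted by an abnormal physical examination, and those obtained after an event that is serious under 6.3 but not graded severe.

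**The case against.** The strongest reply is that Safety (4) may not be an analysis rule. It groups blood pressure with laboratory tests, which after V0 are done only when prompted. It may therefore describe extra testing after an event, leaving the routine readings unrestricted. That reading is tenable. It removes the conflict within the protocol but not the gap in the SAP, which still plans no vital-sign summary. The SAP does not forbid one either, but an unplanned summary is discretionary.

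A reader might infer more than the documents support:

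- **That safety is not compared between arms.** Adverse-event incidence and severity are, and a blood-pressure change that counts as a new or worsened condition would enter that comparison. The gap concerns the recorded vital signs.
- **That readings before and after every session are certain.** This follows from the general rule in Sections 3 and 5.1. The V1 list has no vital signs, and V2 to V6 give no before-and-after timing.
- **That a serious event graded moderate would go uninvestigated.** It might come with an abnormal examination, which is a trigger in Section 2. That section also has systemic events investigated, and Section 6.3 requires follow-up of serious events. Only the gap in the SAP listing is established.
- **That the control arm is lost.** The trigger applies to both arms. What is lost is the randomised comparison in all treated patients.

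**Conclusion.** The point holds for vital signs and for the laboratory listing. Followed as written, the plan would examine routinely recorded blood pressure at most in a subset selected after randomisation, and it plans no by-arm summary of any vital sign. On the more lenient reading of Safety (4), the SAP omission remains.

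The size of the subset is unknown; about 1 to 12 of 60 patients rests on an assumed 2% to 20%. A full summary would estimate an arm difference to within about 0.52 to 0.58 SD per change. That is useful description but not a sensitive test. The count of up to 720 readings depends on the before-and-after rule applying at all six sessions.

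The laboratory mismatch rests on the text alone and needs no assumption. The effect is confined to secondary safety reporting; the primary analysis, sample size and randomisation are untouched.

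**What to change.** 1. **SAP 7.2, vital signs.** Add a descriptive by-arm summary in all treated patients of the change in each vital sign from pre-treatment to 30 minutes after treatment, by session, and from the first available pre-treatment value to V7 and V8. Give the difference and 95% CI, with no formal testing.
2. **Protocol Section 2, Safety (4).** Word it so that its condition does not limit the analysis of routinely recorded blood pressure.
3. **Protocol Section 5.2.** Reconcile the V1 and V2 to V6 lists with Sections 3 and 5.1, so that it is clear when readings are taken.
4. **SAP 7.2, laboratory results.** List every post-baseline result obtained, whatever prompted it, beside its V0 value where one exists.
5. **Triggers.** Reconcile Safety (4) with the SAP listing, and state whether severe or serious is meant. When patients should be tested is a clinical matter that this point leaves to the study team.

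The cost is some wording, one more table and a fuller listing, using data the protocol already has collected under its general rule. The table is large: four vital signs over six sessions plus V7 and V8 give 4 × (6 + 2) = 32 arm differences, to be read with caution and without significance claims.
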